#### **4.3.2.2 Rituximab**

Rituximab will be administered by IV infusion at a dose of 375 mg/m^2 on Day 1 of Cycles 1–6 during induction treatment and on Day 1 of every other month (i.e., every 2 months) during consolidation treatment.

Body surface area (BSA) will be determined at screening and should be used to calculate the dose of rituximab throughout the study unless the patient's weight increases or decreases by > 10% from screening, in which case BSA should be recalculated and used for subsequent dosing. In obese patients (defined as body mass index  $\geq 30$  kg/m^2), there is no BSA cap and actual body weight, not adjusted weight, is recommended. Empiric dose adjustment for obese patients may be implemented per institutional guidelines.

The infusion of rituximab may be split over 2 days if the patient is at increased risk for an IRR (high tumor burden or high peripheral lymphocyte count). Administration of rituximab may be continued on the following day, if needed, for patients who experience an adverse event during the rituximab infusion.

If a dose of rituximab is split over 2 days, both infusions must occur with appropriate premedication (see Section 4.3.2.5) and at the first infusion rate (see Table 6).

Rituximab infusions will be administered according to the instructions in Table 6.

During the treatment period, rituximab must be administered to patients in a setting where full emergency resuscitation facilities are immediately available. Patients should be under close supervision of the investigator at all times.

Rituximab should be administered as a slow IV infusion through a dedicated line. After the end of the first infusion, the IV line or central venous catheter should remain in place for  $\geq 2$  hours in order to administer IV drugs, if necessary. If no adverse events occur after 2 hours, the IV line may be removed or the central venous catheter may be de-accessed. For subsequent infusions, the IV line or central venous catheter should remain in place for at least 1 hour after the end of the infusion. If no adverse events occur after 1 hour, the IV line may be removed or the central venous catheter may be de-accessed.

If a patient tolerates the first cycle of study treatment without significant infusion reactions, rituximab may be administered as a rapid infusion (over 60–90 minutes) in accordance with local institutional guidelines.

**Table 6 Administration of First and Subsequent Infusions of Rituximab**

First Infusion (Day 1 of Cycle 1)	Subsequent Infusions

• Begin infusion at an initial rate of 50 mg/hr.

• If no infusion-related or hypersensitivity reaction occurs, increase the infusion rate in 50-mg/hr increments every 30 minutes to a maximum of 400 mg/hr.

• If a reaction develops, stop or slow the infusion. Administer medications and supportive care in accordance with institutional guidelines. If the reaction has resolved, resume the infusion at a 50% reduction in rate (i.e., 50% of rate being used at the time when the reaction occurred).

	

• If the patient experienced an infusion-related or hypersensitivity reaction during the prior infusion, use full premedication, including 100 mg of prednisone/prednisolone or 80 mg of methylprednisolone or equivalent (until no further IRR occurs); begin infusion at an initial rate of 50 mg/hr; and follow instructions for first infusion.

• If the patient tolerated the prior infusion well (defined by an absence of Grade 2 reactions during a final infusion rate of <math>\geq 100</math> mg/hr), begin infusion at a rate of 100 mg/hr. If no reaction occurs, increase the infusion rate in 100-mg/hr increments every 30 minutes to a maximum of 400 mg/hr.

• If a reaction develops, stop or slow the infusion. Administer medications and supportive care in accordance with institutional guidelines. If the reaction has resolved, resume the infusion at a 50% reduction in rate (i.e., 50% of rate being used at the time when the reaction occurred).

IRR = infusion-related reaction.

No dose modification for rituximab is allowed. Guidelines for treatment delays or discontinuation are provided in Section 5.1.

Premedication with a corticosteroid, analgesic/antipyretic, and antihistamine, as outlined in Section 4.3.2.5, is required to reduce the incidence and severity of IRRs. For anaphylaxis precautions, see Appendix 10.

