**Table 7 Premedication (cont.)**

Timepoint	Patients Requiring Premedication	Premedication	Administration
Cycle 1, Days 8 and 15 (for patients receiving obinutuzumab); Cycles 2 and beyond, Day 1	Patients with no IRR during the previous infusion	
 
Oral analgesic/anti-pyretic medication c
 
	Administer ≥ 30 minutes prior to obinutuzumab or rituximab infusion. For patients receiving rituximab who do not experience any IRR with their previous infusion, premedication may be omitted at the investigator's discretion.
	
 
Patients with Grade 1 or 2 IRR during the previous infusion
 
	
 
Antihistamine drug b
 
Oral analgesic/anti-pyretic c
 
	Administer ≥ 30 minutes prior to obinutuzumab or rituximab infusion.
	
 
Patients with Grade 3 IRR, wheezing, urticaria, or other symptoms of anaphylaxis during the previous infusion
 
	
 
Oral corticosteroid a
 
	Administer ≥ 1 hour prior to obinutuzumab or rituximab infusion.
	
 
Patients with bulky disease
 
	
 
Antihistamine drug b
 
Oral analgesic/anti-pyretic medication c
 
	Administer ≥ 30 minutes prior to obinutuzumab or rituximab infusion.
	Patients at high risk of TLS (see Section 5.1.7.2)	
 
Consider hospitalization if patient is still considered at high risk of TLS (see Section 5.1.7.2), refer to premedication as defined for Cycle 1.
 
	Refer to Section 5.1.7.2.
Cycles 1 to 6	All patients receiving idasanutlin	
 
Second-generation anti-emetic treatments, such as palonosetron, ondansetron, or granisetron
 
	Administer per individual drug prescribing information.
Cycles 1 to 6	All patients	
 
No premedication for diarrhea
 
	Not applicable
	Patients with previous episode of Grade ≥ 3	
 
Loperamide 4 mg orally
 
	Loading dose 30 minutes before first administration of study drug.

---

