**Table 7 Premedication (cont.)**

IRR=infusion-related reaction; TLS=tumor lysis syndrome; ULN=upper limit of normal.

- a Treat with 100 mg of prednisone or prednisolone, 20 mg of dexamethasone, or 80 mg of methylprednisolone. Hydrocortisone should not be used, as it has not been effective in reducing rates of IRR.
- b For example, 50 mg of diphenhydramine.
- c For example, 1000 mg of acetaminophen/paracetamol.
- d Fluid intake of approximately 2–3 L/day. For patients for whom volume overload is considered a significant risk, hospitalization should be considered.
- e Defined as a value above the local laboratory's ULN, or above 476 µmol/L if no local laboratory ULN is available.
- f Laboratory results should be reviewed and electrolyte values should not demonstrate any clinically significant abnormalities prior to the first dose of venetoclax; otherwise, the patient should receive additional prophylactic treatment and hydration prior to the initiation of dosing.

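### After a Grade 1 or 2 rituximab reaction without anaphylaxis features or bulky disease, Table 6 requires a corticosteroid that Table 7 does not list; a Grade 1 reactor who reached 100 mg/hr also has two starting rates

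*Protocol*

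**What the plan says.** Rituximab is given to DLBCL patients in the bridging and expansion cohorts. Protocol Section 4.3.2.2 makes Table 6 the rule for its infusions, and Section 4.3.2.5 makes Table 7 mandatory for premedication.

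Table 6, subsequent infusions:

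- The first bullet applies "If the patient experienced an infusion-related or hypersensitivity reaction during the prior infusion". It sets no grade limit. The site must "use full premedication, including 100 mg of prednisone/prednisolone or 80 mg of methylprednisolone or equivalent (until no further IRR occurs", start at 50 mg/hr and follow the first-infusion ramp.
- The second bullet applies when the prior infusion was tolerated well, "defined by an absence of Grade 2 reactions during a final infusion rate of" at least 100 mg/hr. The start is then 100 mg/hr.
- The text below the table names a corticosteroid, an analgesic/antipyretic and an antihistamine, and says that this premedication, "as outlined in Section 4.3.2.5, is required to reduce the incidence and severity of IRRs".

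Table 7, Day 1 of Cycle 2 and later:

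- "Patients with Grade 1 or 2 IRR during the previous infusion" receive an antihistamine and an oral analgesic/antipyretic, timed before either antibody. No corticosteroid is listed.
- The corticosteroid appears in the next block, for "Patients with Grade 3 IRR, wheezing, urticaria, or other symptoms of anaphylaxis during the previous infusion", apparently together with bulky disease. Footnote a gives the dose: "Treat with 100 mg of prednisone or prednisolone, 20 mg of dexamethasone, or 80 mg of methylprednisolone".
- For rituximab patients "who do not experience any IRR with their previous infusion, premedication may be omitted" at the investigator's discretion.

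**The concern.** Two binding tables give different premedication to the same patient: someone on rituximab with a Grade 1 or 2 reaction at the prior infusion and no wheezing, urticaria, other anaphylaxis symptoms or bulky disease. Table 6 calls for a steroid and Table 7 lists none. Nothing says which prevails, and the sentence under Table 6 points to Table 7's section. A site that takes premedication from there can re-challenge the patient without the steroid. That omission complies with one table and deviates from the other.

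There is also an overlap inside Table 6. The first bullet counts any reaction. The second treats a prior infusion with no Grade 2 reaction as well tolerated, so a Grade 1 reaction does not bar a patient from it. A Grade 1 reactor who finished at 100 mg/hr or faster therefore qualifies under both bullets.

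What is at stake is consistent handling of mild and moderate reactors at re-challenge. Section 5.1.2.1 says most rituximab reactions are of these grades.

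**Working it through.** The plan has no figure to reproduce here. The check sets the instructions side by side, then sizes the difference.

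**Case check** (no wheezing, urticaria, other anaphylaxis symptoms or bulky disease)

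| Prior infusion | Table 6, first bullet | Table 6, second bullet | Table 7 |
|---|---|---|---|
| Grade 2 reaction | Steroid, 50 mg/hr | Does not apply | No steroid listed |
| Grade 1, final rate at least 100 mg/hr | Steroid, 50 mg/hr | 100 mg/hr | No steroid listed |
| Grade 1, final rate below 100 mg/hr | Steroid, 50 mg/hr | Does not apply | No steroid listed |

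Premedication differs in all three rows. The double starting rate arises only in the second.

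Two alternative explanations fail. Table extraction is not the cause: the Grade 1 or 2 row carries its own two drugs and its own timing, and both drugs are listed again after the corticosteroid in the next block. Nor is the row meant for obinutuzumab alone: its timing names both antibodies, and the row above it shows that Table 7 adds a rituximab-specific note where one is wanted.

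**Patients affected (expansion cohort, n = 40).** Section 5.1.2.1 gives an overall reaction rate of at least 10% from general rituximab experience and says most are Grade 1 or 2. It gives no rate for pretreated, premedicated patients. The ranges below are assumptions: a reaction rate of 5% to 30%, and 25% to 90% of reactors in the affected group.

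- Lowest: 40 × 0.05 × 0.25 = 0.5
- At 10%: 40 × 0.10 × 0.25 = 1.0 to 40 × 0.10 × 0.90 = 3.6
- Highest: 40 × 0.30 × 0.90 = 10.8

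Bridging-cohort patients are in scope but not counted. Most reactions occur at the first administration (Section 5.1.2.1), and Table 6 stops the steroid once no reaction recurs. The usual difference is therefore one dose, at Cycle 2 Day 1.

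**Infusion time from the two starting rates.** Assume a BSA of 1.8 m², so 375 × 1.8 = 675 mg, and no further reaction.

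- From 50 mg/hr, rising by 50 every 30 minutes: 25 + 50 + 75 + 100 + 125 + 150 = 525 mg by 3.0 h; the remaining 150 mg at 350 mg/hr takes 0.43 h; total 3.43 h.
- From 100 mg/hr, rising by 100 every 30 minutes: 50 + 100 + 150 + 200 = 500 mg by 2.0 h; the remaining 175 mg at 400 mg/hr takes 0.44 h; total 2.44 h.
- Difference: 3.43 − 2.44 = 0.99 h.

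At a BSA of 1.5 m² (562.5 mg) the times are 3.11 h and 2.16 h. At 2.2 m² (825 mg) they are 3.81 h and 2.81 h. The difference is about one hour throughout.

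**The case against.** The strongest reply is that the two tables can be obeyed together. Table 7 does not forbid a steroid after a Grade 1 or 2 reaction. It is the general table and Table 6 is specific to rituximab, so the natural reading is that Table 6 adds to it. The sentence under Table 6 names a corticosteroid again. A site must also open Table 6 to set the rate, and for a prior reactor the steroid and the 50 mg/hr start stand in the same bullet. Omitting the steroid means using half of that instruction.

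Much of this stands. Giving the steroid satisfies both tables, so on premedication the defect is an omission in Table 7 that a careful site will get past. But the protocol never states that the specific table adds to the general one. The sentence under Table 6 defers to Section 4.3.2.5 for the detail, and Section 4.3.2.1 has a similar sentence for obinutuzumab, so it does not decide the matter. A site that places a Grade 1 reactor under the second bullet meets no steroid instruction there at all.

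The reply does not reach the starting rate. One infusion cannot begin at both 50 and 100 mg/hr.

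Existing safeguards also limit the risk. Resuscitation facilities and close supervision are required, Table 6 has stop, slow and 50% rate-reduction rules, Appendix 10 sets out anaphylaxis procedures, and Section 5.1.2.1 regards Grade 1 or 2 reactions as manageable by slowing or stopping the infusion. These bear on how serious the point is. They do not remove the inconsistency.

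**Conclusion.** The text is inconsistent as written, with a small effect on patient handling only. Table 7 lacks the steroid that Table 6 requires for the group described, and Table 6 gives two starting rates to a Grade 1 reactor whose prior final rate was at least 100 mg/hr. The count of 1.0 to 3.6 of 40 at a 10% reaction rate (0.5 to 10.8 over the wider range) and the one-hour difference rest on the assumed rates and BSA; the inconsistency does not.

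A reader might infer more, and the documents do not support it:

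- *That a Grade 3 reactor may start at 100 mg/hr*, because the definition of good tolerance names only Grade 2. This is over-literal: the first bullet covers every reaction, and a Grade 3 reaction is not a well-tolerated infusion.
- *That the rapid-infusion option in Section 4.3.2.2 is a further defect*, because it does not define a significant reaction. That option is permissive and follows institutional guidelines, so leaving the judgement to the site is a legitimate choice.
- *That trial results are affected.* Section 3.1.2.1 exempts Grade 3 or 4 infusion reactions from the non-hematologic DLT criterion, and the safety summaries in Section 6.4 are descriptive. Premedication already varies by discretion in patients with no prior reaction. There is no effect on complete response, DLTs, the RP2D or any statistical figure.

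**What to change.** Two wording changes:

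1. In Table 7, Grade 1 or 2 row, add: *For rituximab, also give the oral corticosteroid at least 1 hour before the infusion until no further IRR occurs (see Table 6).* Footnote a already carries the same prednisone/prednisolone and methylprednisolone doses as Table 6.
2. In Table 6, leave the first bullet without a grade limit and make the second exclusive of it, by defining good tolerance as *no infusion-related or hypersensitivity reaction and a final infusion rate of at least 100 mg/hr*. State that all other patients start at 50 mg/hr.

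The cost is usually one extra steroid dose for a few patients with mild or moderate reactions, and about one hour more infusion time for Grade 1 reactors who would otherwise have started at 100 mg/hr. Sample size, visits and analyses do not change.

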#### **4.3.2.3 Idasanutlin**

Patients will self-administer idasanutlin tablets PO each day according the schedule of activities (see Appendix 1 and Appendix 2) approximately 15 minutes after eating a meal and with water.

On days when idasanutlin, venetoclax, and obinutuzumab are all given, the order of study treatment administration will be idasanutlin followed by venetoclax and obinutuzumab. Idasanutlin should always be given prior to venetoclax if both drugs are to be administered the same day. If vomiting occurs within 15 minutes of taking idasanutlin, and all expelled tablets are still intact, another dose may be given and the second dose noted in the drug log. Otherwise, no replacement dose is to be given. In cases in which a QD dose of idasanutlin is missed or forgotten, the patient should take the dose as soon as possible, ensuring that the dose is taken within 8 hours of the missed dose with food and water. Otherwise, the dose should not be taken. On days when patients are scheduled to have blood samples collected for PK assessments, the time of each dose of idasanutlin will be recorded to the nearest minute.

Idasanutlin must be stored according to labeled storage conditions.

#### **4.3.2.4 Venetoclax**

Each once-daily dose of venetoclax (per the dose schedule established during dose escalation) will be taken orally with approximately 240 mL of water within approximately 30 minutes after the completion of breakfast or the first meal of the day. A meal containing approximately 30% of the total caloric content from fat is recommended to ensure adequate absorption of venetoclax. The Standard American Heart Association Healthy (Low-Fat) Breakfast includes 1 box cereal (30-40 g), skim milk (240 mL), 1 boiled egg, 1 slice of toast, and margarine (10 g) for approximately 520 Kcal with approximately 17 grams of fat.

On days that venetoclax PK sampling is required, the patient's first meal of the day (e.g., breakfast) should be consumed in the morning at the clinic, and venetoclax dosing should occur in the clinic after completion of the meal to facilitate PK sampling.

On days when idasanutlin, venetoclax, and obinutuzumab are all given, the order of study treatment administration will be idasanutlin followed by venetoclax and obinutuzumab. If vomiting occurs within 15 minutes after taking venetoclax and all expelled tablets are still intact, another dose may be given and the second dose noted in the drug log. If tablets are not identified, or if any are not intact, no replacement dose is to be given. In cases in which a dose of venetoclax is missed or forgotten, the patient should take the dose as soon as possible and ensure that the dose is taken with food and water within 8 hours after the scheduled time of the missed dose. Otherwise, the missed dose should not be taken. On days when patients are scheduled to have blood samples collected for PK assessments, the time of each dose of venetoclax will be recorded to the nearest minute.

Venetoclax must be stored according to labeled storage conditions.

#### **4.3.2.5 Premedication**

Patients must receive premedication as outlined in [Table 7](#).

**Table 7 Premedication**

Timepoint	Patients Requiring Premedication	Premedication	Administration
Cycle 1, Day 1	All patients	Oral corticosteroid a	Administer $\geq$ 1 hour prior to obinutuzumab or rituximab infusion.
	All patients	
 
• Antihistamine drug b
 
• Oral analgesic/anti-pyretic medication c
 
	Administer $\geq$ 30 minutes prior to obinutuzumab or rituximab infusion.
Day 1 of the First cycle including venetoclax	All patients	
 
• Appropriate hydration d
 
	Administer to 24–48 hours prior to the start of venetoclax and continued for at least 24 hours after the first dose.
		
 
• Administration of an oral agent to reduce uric acid, such as allopurinol 300 mg/day, or rasburicase IV, as judged appropriate by the investigator
 
• Rasburicase IV should be administered (unless medically contraindicated) for those patients with elevated uric acid levels e pretreatment
 
	Administer starting 72 hours prior to the first venetoclax dose. If serum uric acid is above ULN administer until normalization of serum uric acid and other laboratory evidence of TLS (e.g., elevated serum LDH levels). f
	Patients considered at high risk of TLS (see Section 5.1.7.2)	
 
• Hospitalization is required for the initial venetoclax dose.
 
	Refer to Section 5.1.7.2.

---

**Table 7 Premedication (cont.)**

IRR=infusion-related reaction; TLS=tumor lysis syndrome; ULN=upper limit of normal.

- a Treat with 100 mg of prednisone or prednisolone, 20 mg of dexamethasone, or 80 mg of methylprednisolone. Hydrocortisone should not be used, as it has not been effective in reducing rates of IRR.
- b For example, 50 mg of diphenhydramine.
- c For example, 1000 mg of acetaminophen/paracetamol.
- d Fluid intake of approximately 2–3 L/day. For patients for whom volume overload is considered a significant risk, hospitalization should be considered.
- e Defined as a value above the local laboratory's ULN, or above 476  $\mu\text{mol/L}$  (8 mg/dL) if no local laboratory ULN is available.
- f Laboratory results should be reviewed and electrolyte values should not demonstrate any clinically significant abnormalities prior to the first dose of venetoclax; otherwise, the patient should receive additional prophylactic treatment and hydration prior to the initiation of dosing.

**Table 7 Premedication (cont.)**

Timepoint	Patients Requiring Premedication	Premedication	Administration
Cycle 1, Days 8 and 15 (for patients receiving obinutuzumab); Cycles 2 and beyond, Day 1	Patients with no IRR during the previous infusion	
 
Oral analgesic/anti-pyretic medication c
 
	Administer ≥ 30 minutes prior to obinutuzumab or rituximab infusion. For patients receiving rituximab who do not experience any IRR with their previous infusion, premedication may be omitted at the investigator's discretion.
	
 
Patients with Grade 1 or 2 IRR during the previous infusion
 
	
 
Antihistamine drug b
 
Oral analgesic/anti-pyretic c
 
	Administer ≥ 30 minutes prior to obinutuzumab or rituximab infusion.
	
 
Patients with Grade 3 IRR, wheezing, urticaria, or other symptoms of anaphylaxis during the previous infusion
 
	
 
Oral corticosteroid a
 
	Administer ≥ 1 hour prior to obinutuzumab or rituximab infusion.
	
 
Patients with bulky disease
 
	
 
Antihistamine drug b
 
Oral analgesic/anti-pyretic medication c
 
	Administer ≥ 30 minutes prior to obinutuzumab or rituximab infusion.
	Patients at high risk of TLS (see Section 5.1.7.2)	
 
Consider hospitalization if patient is still considered at high risk of TLS (see Section 5.1.7.2), refer to premedication as defined for Cycle 1.
 
	Refer to Section 5.1.7.2.
Cycles 1 to 6	All patients receiving idasanutlin	
 
Second-generation anti-emetic treatments, such as palonosetron, ondansetron, or granisetron
 
	Administer per individual drug prescribing information.
Cycles 1 to 6	All patients	
 
No premedication for diarrhea
 
	Not applicable
	Patients with previous episode of Grade ≥ 3	
 
Loperamide 4 mg orally
 
	Loading dose 30 minutes before first administration of study drug.

---

**Table 7 Premedication (cont.)**

IRR=infusion-related reaction; TLS=tumor lysis syndrome; ULN=upper limit of normal.

- a Treat with 100 mg of prednisone or prednisolone, 20 mg of dexamethasone, or 80 mg of methylprednisolone. Hydrocortisone should not be used, as it has not been effective in reducing rates of IRR.
- b For example, 50 mg of diphenhydramine.
- c For example, 1000 mg of acetaminophen/paracetamol.
- d Fluid intake of approximately 2–3 L/day. For patients for whom volume overload is considered a significant risk, hospitalization should be considered.
- e Defined as a value above the local laboratory's ULN, or above 476 µmol/L if no local laboratory ULN is available.
- f Laboratory results should be reviewed and electrolyte values should not demonstrate any clinically significant abnormalities prior to the first dose of venetoclax; otherwise, the patient should receive additional prophylactic treatment and hydration prior to the initiation of dosing.

